Recruitment. Participants will be recruited through our established partnership with the Neurodevelopmental Service clinics at SSCY Centre, including the Child Development Clinic and Manitoba FASD Centre. Individuals identifying as primary caregivers to children with additional health, developmental or behavioural needs will be invited via the SSCY “consent to contact” process and/or via social media postings (see attached social media infographic examples in Appendix A). Social media postings will be posted across Hearts & Minds Lab accounts (See Appendix A). Additionally, we will also be asking participants to share our study

and contact information with other prospective participants so that prospective participants can contact us if interested. There will be clear communication to ensure that families understand that project participation will not affect their other services at SSCY. In addition to SSCY we plan to reach out to other local Manitoba organizations (St.Amant, KIDTHINK, MATC) to recruit through their processes after approval is gained.

Consent. Recruited parents/caregivers will click on a link to take part in the eligibility screener via REDCap (sent out via email with recruitment information from the local Manitoba organization, or in response to email correspondence from potential participants from social media postings). When participants click on the link for the eligibility screener, they will see the consent form first, and will be required to click “agree” or “disagree” to consent prior to starting the survey on REDCap. When eligible participants are redirected from the eligibility screener to the pre-questionnaire, they will first see a more detailed study specific consent form at the start of the online pre-questionnaire. This consent form will also be provided at the start of the follow-up and post-questionnaires. This consent form will be attached to the first page of the online REDCap survey. Participants will read the consent form and will respond to it with the click of a button to indicate if they would like to “agree” or “decline” to participate. They may also decline to participate by simply closing the browser prior to starting or at any point throughout the survey. Additionally, consent will also be discussed at the start of the session for participants randomized to the SSI group.

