Participant Involvement in Study. For a flowchart of participant contact points please see attachment ‘SPYKids Points of Contact’ in Appendix D. After completing the online eligibility screener, those who are ineligible will also be automatically sent a compassionate email via REDCap informing them that they are not eligible, with a resource list of mental

health, crisis, and parenting resources. Contact information for the research team will also be included should they have any questions regarding eligibility. Participants who are eligible will be informed via REDCap and automatically sent to the pre-questionnaire. Participants will be screened using questions (e.g., “Are you currently on a waitlist for accessing services for your child?”). Please see Appendix C for REDCap the Eligibility Screener.

Quick Summary of Participant Contact Points if eligible (N=70):

1. Participants will read the main program consent form.
2. If they agree to consent, participants will begin the online pre-questionnaires.
3. Following the pre-questionnaires participants will be randomized to either SAU or SSI group via ID# using an online tool (randomizer.org) and will be notified via email of what group they have been randomized to.
4. Participants randomized to the SSI Group (n=35) will take part in the 90-minute SSI via telehealth, the post-questionnaires immediately post intervention and the 2 follow up questionnaires (2 weeks after the SSI and 3 months after the pre-questionnaire) to assess maintenance effects. Immediately following randomization, participants will be sent an email with an invitation to book a time for the SSI using Microsoft Bookings, a University of Manitoba App part of the Microsoft 365 suite of apps. Participants in this group will also receive a follow-up email from the clinical coach 1-week following the SSI.
5. Participants randomized to the SAU group (n=35) will receive services as usual on the SCCY waitlist, as well as receive a list of psychological and family support services. They will also participate in the eligibility screener, pre-questionnaires, the 2-week post questionnaires, and 3-month post follow-up questionnaires.

Further Details on Project Components:

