SPYKids Consultation (SSI) (n=35): Within the pre-questionnaire, a family needs assessment via REDCap will identify parent areas of primary concern across child mental health and psychosocial resource needs (Appendix C). An MA-level trainee (supervised) or PhD-level trainee with clinical experience will review a summary of needs compiled by the project coordinator and then meet with the family in a 1.5-hour session. Sessions will be tailored to identified needs based on materials developed with the parent advisory panel, service providers, and the research team. Content will include psychoeducation, identification of 1-2 skills to address a primary mental health issue, brief practice of the skills, and specific plan to apply the skills at home to obtain a quantifiable reduction in symptom frequency over time. This will be done utilizing handouts created via our research team and guided/reviewed by clinical psychologists (Drs. [name] and [name]) to employ best-practices in promoting positive parent-child relationships and reducing parenting stress (See Appendix D). Lastly, families will be provided with specific recommendations for relevant services and informal supports from our family-focused resource list (Appendix D). As mentioned above, the purpose of the SSI is not to completely resolve challenges, but to provide parents with some help, encouragement, and motivation in the interim while waiting for other services. Around one week after participants attend the single session, they will receive a customized email summarizing what was discussed during the session by the clinical coach to build motivation (informed by [name] methodology).

The study will take place online, through Zoom Healthcare, REDCap, and through emailing with the research team and community organizations regarding support with recruitment procedures. Recruitment may take place at a variety of community-based services through postering, through email listservs, or talks by the research team.

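### Participant referral combined with individual randomization opens an unmeasured route for SSI content to reach SAU families; the size is unknown and probably modest, and the safeguards cost little.

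*Combined protocol and SAP*

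**What the plan says.** Under Design & Study Procedures, Recruitment, the main sources are the SSCY clinics ("Participants will be recruited through our established partnership with the Neurodevelopmental Service clinics at SSCY Centre") and social media. Referral by participants is an added route: "Additionally, we will also be asking participants to share our study". The people reached this way, other would-be participants, are then expected to approach the team themselves. The text does not say at what stage participants are asked, or what share of the sample is expected this way.

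Item 3 of the participant contact points says that after the pre-questionnaires "participants will be randomized to either SAU or SSI group via ID" number, and that participants are told their group by email. Nothing links, stratifies or co-allocates families who know each other. The target is 70 randomized, 35 per arm.

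The SPYKids Consultation section describes a 90-minute coach-led session tailored to the family. On written material it says "This will be done utilizing handouts created via our research team", and that about a week later "they will receive a customized email summarizing what was discussed during the session by the clinical coach". SSI families also get service recommendations from a resource list. SAU families stay on the waitlist and receive a list of psychological and family support services (item 5).

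Statistical Analyses compares change in child mental health between arms, adjusted for baseline score and child age, and treats parenting stress and parent mental health similarly. No referral, exposure or cluster term is mentioned.

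**The concern.** Asking participants to bring in others builds acquaintance links into the sample, and individual allocation then places many of those links across the two arms. An SSI parent can forward an email, and can pass on handouts if they are kept. A SAU parent who uses that content may improve for the same reason as the SSI arm, which moves the SPYKids-SAU difference toward zero. A parent referred after the referrer's own session might also meet the content before completing the pre-questionnaire.

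The comparison at stake is the one that Statistical Analyses calls primary (child mental health), together with the parent outcomes. If it came out null, the body text offers no means of judging whether contamination played a part. A pilot is also the natural place to learn whether individual randomization works in this community, and without a referral or exposure item it would not.

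**Working it through.** **The plan's own figure.** There is no power statement, effect size, dropout rate or contamination allowance to reproduce. Only the arithmetic 2 × 35 = 70 can be checked, and it is right.

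**Inputs from the documents.** 35 per arm; individual allocation; significance level 0.05.

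**Inputs assumed.** Two-sided testing. A standardized effect d = 0.5, chosen because the background calls the effects of single-session interventions medium; it is not a planning value. Let q be the share of participants who belong to a linked pair (10%, 20% or 40%), and e the fraction of the SSI effect that a linked SAU parent obtains (0.5 for the main illustration).

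**Step 1: chance that a linked pair is split.** With 35/35 allocation, a given parent's partner falls in the other arm with probability 35/69 = 0.507.

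**Step 2: share of SAU parents linked to an SSI parent.** c = q × 35/69.

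**Step 3: shrinkage.** Observed d = 0.5 × (1 − c × e).

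**Step 4: power.** Two-sample t test, 35 per arm, no baseline adjustment.

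| q | c | SAU parents linked (of 35) | Shrinkage at e = 0.5 | Observed d | Power |
|---|---|---|---|---|---|
| 0 | 0 | 0 | 0 | 0.500 | 54% |
| 10% | 5.1% | 1.8 | 2.5% | 0.487 | 52% |
| 20% | 10.1% | 3.6 | 5.1% | 0.475 | 50% |
| 40% | 20.3% | 7.1 | 10.1% | 0.449 | 46% |

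If nothing is transferred (e = 0), the shrinkage is zero in every row.

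**Another way to count.** Suppose instead that 10-30% of the 70 enter by participant referral, each adding one link. Split links number 70 × 0.10 × 0.507 = 3.6 to 70 × 0.30 × 0.507 = 10.7. Divided by 35, that is 10% to 30% of SAU parents if no SAU parent is counted twice. With e from 0.5 to 1, shrinkage runs from 0.101 × 0.5 = 5% to 0.304 × 1 = 30%, and unadjusted power falls to between 50% and 30%. The upper end needs both a high referral share and full transfer of the benefit.

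**Baseline adjustment.** The planned model adjusts for the baseline score. With an assumed correlation of 0.6, power at d = 0.5 is 73% with no dilution.

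**The case against.** The strongest reply is that the documents show a possibility, not an event. They give no referral rate, no sharing rate and no timing for the request. That referred parents are acquaintances, and that parents keep the handouts, are inferences; only the summary email is expressly sent to them. The session is coached, practised and tailored to one family's needs, so second-hand paper is unlikely to carry its full effect. Time order matters too: where a SAU parent is the referrer, the SSI parent enrols later, and content may arrive after the first SAU follow-up. All of this stands, and it is why the upper end of the range above should not be taken as the expected size.

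A reader might infer that the contrast is in fact diluted and that nothing could detect it. The documents support neither. Dilution requires split pairs, sharing and use of the content, and none of these is quantified. The screener and questionnaires are in Appendix C, which was not available, so a relevant item there cannot be ruled out. Nor is the control arm meant to go without everything the SSI arm gets: SAU families receive a services list of their own.

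The reach is also limited. Aims and Hypotheses names feasibility and acceptability as primary, through coach fidelity and parent satisfaction, and SAU exposure touches neither. Statistical Analyses, however, names child mental health as primary, and Aims and Hypotheses also describes primary analyses of child well-being between arms. Those comparisons would be affected. At 35 per arm, limited power is a larger problem than plausible dilution, but it does not remove the bias or make it visible.

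**Conclusion.** A contamination route exists: participant referral, individual open allocation, and written SSI content, with no safeguard or measurement in the body text. Any effect would bias the child and parent outcome comparisons toward zero. The size is unknown. With 10-40% of participants in linked pairs and half the effect transferred, the difference would shrink by about 2.5-10%, and unadjusted power at d = 0.5 would fall from 54% to about 46-52%. These figures rest on assumed values of q, e and d, and only indicate scale.

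This is a minor point. It merits action because the safeguards are nearly free and would make a null result easier to read.

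**What to change.** 1. Keep the referral route. Make the sharing request at the screener or pre-questionnaire stage, before allocation, and limit it to the study link and contact information. Deferring it to each parent's 3-month survey would nearly close the route, since Timeline & Budget has recruitment starting in November 2022 and sessions ending around February 2023.
2. In the session script and the 1-week email, ask SSI parents not to pass SPYKids handouts or the summary to other families who may be in the study until follow-up ends.
3. Unless Appendix C already has them, add a screener item on whether a participant told the parent about the study and, where known, who. Add one item to both arms' follow-up surveys on whether another family has shared SPYKids content.
4. Keep the as-randomized analysis primary. Report the exposure rate in SAU as a feasibility result. Add a supportive sensitivity analysis that excludes participant-referred parents from both arms; excluding them from SAU only would break comparability. Use reported exposure descriptively, because it arises after randomization.

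Cost: two short survey items, a line in the script and email, and possibly slightly fewer referrals from parents who would have shared later.

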through a single session consultation model. SPYKids has been designed for families on waitlists at local organizations, such as Specialized Services for Children and Youth (SSCY), St. Amant, MATC, and KIDTHINK. The purpose of this single-session intervention (SSI) is not to completely resolve challenges, but to provide parents with some help, encouragement, and motivation in the interim while waiting for more comprehensive services. A parent advisory panel and service providers have informed program development aligned with parent-driven priorities that enhance quality of care and long-term child outcomes (PSREB Approval P2020:064 at the University of Manitoba; Ref # 2013 at SSCY). Team expertise has informed the creation of a program that complements existing services and has sustainable impacts on child well-being. Now we seek to conduct a pilot randomized control trial on the SPYKids program. Our main goals are to determine the feasibility and acceptability of the SPYKids Program compared to services as usual (SAU; provincial waitlists for assessments or services, including SSCY service waitlists). We are also interested in changes in parenting stress, mental health, and parent and child well-being between the SPYKids and SAU groups before and after the SSI.

Project Description

Background and Rationale

Neurodevelopmental disorders, including attention deficit hyperactivity, autism, and fetal alcohol spectrum disorders, are experienced by 7-14% of Canadian children and represent the leading cause of disability in childhood.¹ Symptoms of NDDs, such as difficulties with communication and impulsivity, are linked to impaired quality of life, with commonly co-occurring behaviour and emotional (i.e., mental health) problems exacerbating the burden of illness.² In fact, emergent mental health problems are more closely linked to family distress than

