The objective of this study is to assess the feasibility and acceptability of an SSI (i.e., SPYKids) for parents on local Manitoban service and program waitlists who have children with health, behavioural, and developmental needs. This objective will be divided into Primary and Secondary outcomes.

1. Primary Outcomes: [FEASIBILITY & ACCEPTABILITY]:

Primary outcomes are aimed at determining the feasibility and acceptability of SPYKids compared to SAU. This will be done through monitoring of both clinical coach adherence to protocols via a fidelity checklist and parent satisfaction of the overall SSI via feedback questionnaires including both scaled responses and open-ended responses, using both quantitative and qualitative methodology. Parent feedback of the SSI will be assessed using the Program Feedback Scale²⁰ (adapted from [name] research), and the feedback questionnaire, which was created by researchers in the lab for the purposes of this study. Please see the attached Appendix C for all questionnaires.

2. Secondary Outcomes:

Secondary outcomes include metrics of parenting stress and mental health between the SPYKids and SAU groups before and after the SPYKids session. Other exploratory outcomes will include both parent and child well-being.

- Parent well-being: Secondary outcomes related to parent well-being will be changes in parenting stress (Parenting Stress Index²¹) and parent mental health

(Patient Health Questionnaire-9²², Generalized Anxiety Disorder – 7 item scale²³, PROMIS Anger - Short Form²⁴). Exploratory outcomes include changes in hope (Beck Hopelessness Scale-4²⁵), Perceived control/agency²⁶, Readiness to change (Readiness Ruler²⁷), and Problem Solving²⁶.

- Child well-being: Primary analyses will compare changes in child well-being scores (Strengths & Difficulties Questionnaire²⁸) between the SPYKids vs SAU groups. Secondary analyses will examine persistence of these effects at the 3-month follow-up.

Research Methods

Participants

We plan to recruit 70-140 participants and hope to randomize 70 participants to either the SAU or SSI groups (n= 35 per condition). In order to be eligible to participate, they must have a residence in Manitoba, be at least 18 years old, must identify as a primary caregiver to a child who is 2-5 years old, and the child must be on a waitlist for Neurodevelopmental Services in Manitoba (See Eligibility Screener in Appendix C).

Design & Study Procedures

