Across all self-report questionnaire outcomes, measures have excellent reliability and validity. This includes established cut-offs indicating mental health problem severity needs therapeutic services with high sensitivity/specificity to diagnostic interviews. Constructs with established tools from consortium agreements, per the COMET (Core Outcome Measures in Effectiveness Trials) Initiative are prioritized.²⁹

Primary outcome. Child mental health. The primary analyses will compare the change in child mental health symptom scores between (a) the SPYKids vs SAU group at $p=0.05$ using a linear model for the change, accounting for pre-intervention scores and important covariate of child age. Secondary analyses will examine persistence of these effects at the 3-month-follow-up by examining the time-by-intervention interactions in a linear mixed-effects model accounting for within-subject serial correlations, and between-subject effects of the intervention and age.

Secondary outcomes. Parenting stress & mental health. We will use similar linear mixed-effects models for the analysis of key secondary outcomes.

Exploratory outcomes. Parent Self-Efficacy. Exploratory analyses (SPYKids only) will assess the extent to which dimensions of parenting self-efficacy (hope,²⁵ agency,²⁶ readiness to change²⁷) immediately following the intervention are associated with primary and secondary change. This will inform how immediate post-treatment progress is linked to subsequent improvements in well-being. Parent Satisfaction will be assessed to determine if key benchmark

acceptability is met 3.5/5 on an established scale.²⁰ Participants will complete open-ended text-based items allowing them to express their views on the intervention content, their engagement with this content, their satisfaction with their involvement in the intervention, and suggested improvements. Open-ended text items will be analyzed using thematic analysis.³⁰

General considerations. In general, p-values < .05 will be considered statistically significant, without controlling for multiple inference. Complete-case methods will be used for planned analyses; however, sensitivity analyses may be used to examine the impacts of imputation on conclusions, should the usual assumptions appear to be met (MAR, missing at random, or MCAR, missing completely at random). Data will be stored in REDCap following Good Clinical Practices.³¹ Analyses will be done in R v.4.0.0 and the lme4 package v 1.1-26.35

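### The Aims section makes feasibility and acceptability the primary outcomes, Statistical Analyses makes child mental health primary, and nothing reconciles the two

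*Combined protocol and SAP*

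**What the plan says.** The introductory summary states: "Our main goals are to determine the feasibility and acceptability of the SPYKids Program compared to services as usual". Aims and Hypotheses opens in the same way, "The objective of this study is to assess the feasibility and acceptability of an SSI", and its item 1 reads "Primary outcomes are aimed at determining the feasibility and acceptability of SPYKids compared to SAU". That item measures the primary outcomes by a checklist of coach adherence and by parent feedback, both scaled and open-ended, using quantitative and qualitative methods. For the scaled part, "Parent feedback of the SSI will be assessed using the Program Feedback Scale" (reference 20), alongside a feedback questionnaire built by the lab. Child well-being, measured by the Strengths & Difficulties Questionnaire (SDQ), comes under item 2, Secondary Outcomes. The sentence introducing that item calls it exploratory, yet its own bullet speaks of primary analyses.

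The Statistical Analyses section sets out a different order. It begins "Primary outcome. Child mental health. The primary analyses will compare the change in child mental health symptom scores", compared between SPYKids and services as usual (SAU) at p=0.05 in a linear model adjusted for baseline score and child age. Parenting stress and mental health follow as secondary outcomes. Under the exploratory heading come the self-efficacy analyses, the satisfaction benchmark ("acceptability is met 3.5/5 on an established scale", also reference 20) and the thematic analysis of open-ended items. Fidelity does not appear.

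**The concern.** A plan has to say before the data are seen which result carries the conclusion. This one gives two answers. A report that followed the Aims section would lead with fidelity and parent satisfaction. A report that followed Statistical Analyses would lead with a significance test on child symptoms. Each could cite the plan as its authority.

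The risk runs both ways. A favourable child result could be presented as the prespecified primary finding of a trial set up to study feasibility and acceptability. A non-significant one could be presented as a failed primary, although the stated objective never depended on it. An analyst working only from Statistical Analyses could also finish without reporting fidelity, which the Aims section lists first among its primary measures.

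**Working it through.** No figure in the plan bears on this, so the check is a comparison of the sections.

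| Item | Introductory summary; Aims and Hypotheses | Statistical Analyses |
|---|---|---|
| Feasibility and acceptability as a whole | Main goals, study objective, primary outcomes | No entry under the primary heading |
| Coach fidelity checklist | Primary measure | Not mentioned; no estimate, no criterion |
| Scaled parent feedback (reference 20) | Primary measure | 3.5/5 benchmark, under the exploratory heading |
| Open-ended parent feedback | Primary measure, qualitative method | Thematic analysis, under the exploratory heading |
| Child outcome | Under Secondary Outcomes; introduced as exploratory; bullet says primary analyses | Primary outcome, tested at p=0.05 |

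1. *Is the word primary in Statistical Analyses a stray label?* The section moves from a primary to a secondary to an exploratory heading. Its exploratory paragraph then asks whether self-efficacy dimensions "are associated with primary and secondary change". A primary outcome that changes over time fits the child score; it does not fit a fidelity checklist or a satisfaction rating given after a session. The label is used consistently within the section.

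2. *Does any text join the two hierarchies?* None that is visible. Co-primaries are not declared and neither section is said to prevail. Appendix C is not shown, but the Measures section describes it as a table and copies of questionnaires. Whatever it lists, the two sections still disagree.

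3. *Which steps are inferred?* Three. The exploratory rank of the benchmark comes from its place under that heading; the sentence itself calls the benchmark key. The identity of the benchmark scale with the Program Feedback Scale comes from the shared reference 20, since Statistical Analyses does not name the scale. The identity of the child outcome with the SDQ comes from its being the only child measure named in Aims. The central conflict needs none of the three: child mental health is not a primary outcome in Aims under any instrument.

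4. *Can the primary outcomes in Aims be compared with SAU?* Coach fidelity and feedback on the session exist only where there was a session. By the contact-point summary and the time-commitment paragraph, SAU participants have no session and no post-session questionnaire. The comparison in item 1 cannot apply to those measures.

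5. *Is the benchmark usable as a primary criterion?* Not yet. The plan does not say whether the mean, or its lower confidence limit, must reach 3.5. As an illustration, assume all 35 SPYKids parents respond and the SD is 0.7 (the plan gives none). The 95% half-width is t(0.975, 34) × SD/√n = 2.03 × 0.7/√35 = 0.24. A mean of 3.6 then has a lower limit of 3.6 − 0.24 = 3.36, which passes one rule and fails the other. For SDs of 0.5 to 1.0 the half-width is 0.17 to 0.34.

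**The case against.** The best rival reading is a drafting slip. The child bullet in Aims and the primary paragraph in Statistical Analyses share a pattern: primary analyses compare change by arm, secondary analyses look at persistence to three months. In both places primary may have been meant to rank time points within the child domain. That is plausible for the Aims bullet and makes an oversight more likely than a considered second hierarchy. It does not rescue Statistical Analyses, which says primary outcome and builds its lower tiers beneath it.

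Four stronger readings are tempting, and the documents do not support them.

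- *The plan expressly demotes acceptability to exploratory.* It does so only by position, and it calls the benchmark key.
- *The absence of multiplicity control causes the conflict.* The plan does say that results at p < .05 are "considered statistically significant, without controlling for multiple inference". But the 3.5/5 benchmark carries no p-value, so an adjustment would not rank it against the child test. Each section does rank its outcomes; the ranks disagree.
- *The two candidates would often give opposite headlines.* Good satisfaction and no significant child effect are different findings and can both be true. Any frequency would be one minus an assumed power. The plan gives no numerical effect size (only a mention of medium effects in the background), no SD, no attrition rate and no sidedness for the test. The calculation would also need satisfaction to be independent of the child result.
- *The sponsor means to choose the primary afterwards.* Nothing in the text suggests this. The point is that the plan as written would permit it.

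**Conclusion.** The contradiction is real and should be fixed. On their plain words, the introductory summary and Aims make feasibility and acceptability primary, and Statistical Analyses makes child mental health primary. The conclusion rests on those words alone and on no assumed effect size, SD or dropout rate. Its size is not a number: it decides which result is the trial's headline, and it leaves one stated primary measure, fidelity, with no analysis.

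The double rank of the satisfaction scale and the link between the child outcome and the SDQ are reasonable inferences and should be put to the sponsor as such.

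**What to change.** Use one outcome hierarchy in the introductory summary, Aims and Hypotheses, and Statistical Analyses. Following the stated main goals:

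1. In Statistical Analyses, make feasibility and acceptability primary. Move both the 3.5/5 benchmark and the thematic analysis there; moving only the benchmark would leave part of the conflict in place. Name the scale. Report the mean with a 95% CI and the number responding out of those randomized to SPYKids. State in advance whether the mean or its lower confidence limit is compared with 3.5.
2. Add an estimate with a 95% CI for checklist fidelity.
3. Give the child outcome one non-primary rank in both sections, secondary or exploratory as the sponsor chooses. Name its instrument in Statistical Analyses, remove the primary-analyses wording from the Aims bullet, and report an adjusted between-arm difference with a 95% CI.
4. Limit the comparison with SAU to measures that both arms have.

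If the sponsor prefers child mental health as primary, or wants declared co-primaries, all three places should say so and every other outcome should have a stated rank.

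The cost is text edits and a short fidelity analysis; no participants or questionnaires are added. Under the first option child mental health is no longer the headline test. Timeline & Budget schedules sessions from November 2022 to about February 2023. If outcome data have already been seen, the re-ranking must be disclosed as not prespecified.
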